## 2 Statistical methods

### 2.1 Data analysis general information

Summary statistics for continuous variables will include N, mean, standard deviation, minimum, lower quartile, median, upper quartile, and maximum. Summary statistics for discrete variables will be presented in the number and percent of subjects in each category.

If not otherwise specified, p-values will be presented as two-sided p-values, and two-sided confidence intervals will be displayed.

The default level of significance will be set to 5% (two-sided, family-wise type I error).

Data analyses will be presented by treatment regimen. Efficacy and safety data will be presented by the following 3 treatment groups.

- Secukinumab 150 mg
- Secukinumab 300 mg
- GP2017 40 mg

### 2.2 Analysis sets

The following analysis sets will be used in this study:

**Randomized set:** The randomized set will be defined as all subjects who were randomized. Unless otherwise specified, mis-randomized subjects (mis-randomized in IRT) will be excluded from the randomized set.

Mis-randomized subjects are defined as those subjects who were mistakenly randomized into the IRT prior to the site confirming all eligibility criteria had been met and to whom no study medication was given. Mis-randomized subjects are treated as screen failures.

**Full analysis set (FAS):** The FAS will be comprised of all subjects from the randomized set to whom study treatment has been assigned. Following the intent-to-treat principle, subjects will be evaluated according to the treatment assigned at randomization.

**Safety set:** The safety set includes all subjects who took at least one dose of study treatment during the treatment period. Subjects will be evaluated according to treatment received.

**Syndesmophyte Subset:** The syndesmophyte subset will include all subjects in the FAS who have syndesmophyte at baseline. A subject with at least one individual vertebral score  $\geq 2$  for any of the interpretable locations will be classified as having a syndesmophyte.

**MRI Subset:** The MRI subset will include all subjects in the FAS who have an MRI performed at the selected centers.

### **2.2.1 Subgroup of interest**

The primary endpoint(s) and secondary endpoints will be evaluated by gender and by smoking status. Subjects with missing data in a subgroup category will be omitted for the corresponding subgroup analysis.

## **2.3 Subject disposition, demographics and other baseline characteristics**

### **2.3.1 Subject disposition**

The number of subjects screened will be presented. In addition, the reasons for screen failures will be provided. The number and percentage of subjects in the randomized set who completed the study periods and who discontinued the study prematurely (including the reason for discontinuation) will be presented at the end of the treatment period and follow-up period, for each treatment group and all subjects.

For each protocol deviation (PD), the number and percentage of subjects for whom the PD applies will be tabulated by deviation category. If not reported separately, this includes the PDs related to COVID-19.

### **2.3.2 Background and demographic characteristics**

The following common background and demographic variables will be summarized:

- Gender, age, race, ethnicity, weight, height, and BMI.

Baseline disease characteristics will also be summarized for the following variables:

- Subject's global assessment of disease activity and other ASAS components, hsCRP, use (yes/no) and separate dose of MTX (mg/week), sulfasalazine (g/day) and systemic corticosteroids (mg/day) at randomization, time since first diagnosis of AS (years), modified New York criteria for AS, mSASSS, number of syndesmophytes, HLA-B27, total back pain (VAS), nocturnal back pain (VAS), total BASDAI score and spinal pain (BASDAI question #2).

### **2.3.3 Medical history**

A history of AS with focus on previous extra-articular involvement and past therapies for AS will be obtained. Any other significant prior or active medical condition at the time of signing informed consent will be recorded and coded using the MedDRA dictionary. These medical conditions will be summarized by primary system organ class and preferred term.

To establish a baseline level of cardiovascular risk, the number and percentage of subjects with pre-solicited cardiovascular risk factors will be summarized by treatment group. The number of cardiovascular risk factors that each subject has will also be summarized by treatment group. If it is unknown whether or not a subject currently or previously experienced a specific cardiovascular risk factor, it will be assumed that cardiovascular risk factor did not occur for that subject.

Smoking history will be summarized by treatment group.

## **2.4 Treatments (study treatment, rescue medication, concomitant therapies, compliance)**

### **2.4.1 Study treatment / compliance**

The analysis of study treatment data will be based on the safety set. The number of visits with injections received will be presented by treatment group.

The duration of exposure to study treatment will also be summarized by treatment group. In addition, the number and percentage of subjects with cumulative exposure levels (e.g., any exposure,  $\geq 2$  weeks,  $\geq 4$  weeks,  $\geq 8$  weeks, etc.) will be presented.

Duration of exposure of a treatment will be defined as the time from first dose of the treatment to the minimum of (last dose of the treatment + 84 days) and (last visit date).

Duration of exposure of a treatment for the pre- and during COVID-19 pandemic periods will be defined as the duration of exposure of a treatment that fell into the pre- and during COVID-19 pandemic periods, respectively. These periods are defined in [Section 2.15.1](#).

Duration of exposure (years) = duration of exposure (days) / 365.25.

Duration of exposure (100 subject years) = duration of exposure (years) / 100.

The analyses of duration of exposure described above will be done for the entire study treatment period.

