Subjects who prematurely discontinue the study treatment (secukinumab or GP2017) are encouraged to remain in the study to continue the study-related assessments until the completion of the study at Week F120. Every effort should be made to request the subjects to complete the final X-ray evaluations as part of the Week 104 visit assessments. Please refer to [Section 5.6.2](#) for reasons for study treatment discontinuation.

Subjects who prematurely discontinue completely from the study for any reason should return for the final visit to conduct the Week 104 assessments (4 weeks after the last study treatment administration of secukinumab or 2 weeks after the last study treatment administration of GP2017), as well as return for the follow-up visits (Week F112 and F120). Every effort should be made to request discontinued subjects to complete the final X-ray and MRI evaluations as part of the Week 104 visit assessments, unless the last X-ray and/or MRI was taken within 12 weeks prior to discontinuation.

At the final visit, all dispensed investigational product should be reconciled and the adverse event and concomitant medications reconciled on the CRF.

If the subject refuses to return for these assessments or is unable to do so, every effort should be made to contact him/her or a knowledgeable informant by telephone to determine the reason. Attempts to contact the subject should be recorded in the source documentation.

Table 6-1 Assessment schedule – Part 1: Screening to Week 52

Period	Screening			Treatment																											
	SV1 -10 to -4	SV2 -4 to BSL	BSL	1	2	3	4	6	8	10	12	14	16	18	20	22	24	26	28	30	32	34	36	38	40	42	44	46	48	50	52
Optional site visit				X	X	X		X	X	X		X		X	X	X		X	X	X	X	X	X	X		X	X	X	X	X	
Obtain informed consent	X																														
Inclusion/ Exclusion criteria ¹	X	X	X																												
Relevant medical history/ current medical condition	X	X	X																												
Prior medication	X	X	X																												
High sensitivity C-reactive protein (hsCRP)	X		X																												
X-ray of SI joints ²	X ⁴																														
X-ray (cervical + thoraco- lumbar) for mSASSS ²	X ^{3,4}		X ^{3,4}																												
Local PPD skin test ⁵ or Central laboratory test for tuberculosis screening	X																														
AS disease assessment ⁶		X																													
Demography		X																													

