7.2.2 SAE reporting

To ensure subject safety, every SAE, regardless of causality, occurring after the patient has provided informed consent and until 20 weeks following the last administration of study treatment or until the end of study visit (whichever is later) must be reported to Novartis safety/CRO within 24 hours of learning of its occurrence. Any SAEs experienced after this period should only be reported to Novartis if the investigator suspects a causal relationship to study treatment.

All follow-up information for the SAE including information on complications, progression of the initial SAE and recurrent episodes must be reported as follow-up information to the original episode within 24 hours of the investigator receiving the follow-up information. An SAE occurring at a different time interval or otherwise considered completely unrelated to a previously reported one must be reported separately as a new event.

Information about all SAEs is collected and recorded on the Serious Adverse Event Report Form; all applicable sections of the form must be completed in order to provide a clinically thorough report. The investigator must assess the relationship of each SAE to each specific component of study treatment, (if study treatment consists of several components) complete the SAE Report Form in English, and submit the completed form within 24 hours to Novartis. Detailed instructions regarding the submission process and requirements for signature are to be found in the investigator folder provided to each site.

Follow-up information is submitted as instructed in the investigator folder. Each re-occurrence, complication, or progression of the original event must be reported as a follow-up to that event regardless of when it occurs. The follow-up information should describe whether the event has resolved or continues, if and how it was treated, whether the blind was broken or not, and whether the subject continued or withdrew from study participation.

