9.5.3 Safety variables

Adverse events

Treatment-emergent adverse events (events started after the first dose of study treatment or events present prior to the first dose of study treatment but increased in severity based on preferred term) will be summarized.

Adverse events will be summarized by presenting, for each treatment group, the number and percentage of subjects having any AE, having an AE in each primary system organ class and having each individual AE (preferred term). Summaries will also be presented for AEs by severity and for study treatment related AEs. If a subject reported more than one adverse event with the same preferred term, the adverse event with the greatest severity will be presented. If a subject reported more than one adverse event within the same primary system organ class, the subject will be counted only once with the greatest severity at the system organ class level, where applicable. Serious adverse events will also be summarized.

As appropriate, the incidence of AEs will be presented per 100 subject years of exposure.

[REDACTED]

Separate summaries will be provided for death, serious adverse event, other significant adverse events leading to discontinuation and adverse events leading to dose adjustment (including study treatment discontinuation).

A graphical display of relative frequencies within system organ classes and relative risks, as appropriate, will be presented.

[REDACTED]

Laboratory data

The summary of laboratory evaluations will be presented for three groups of laboratory tests (hematology and serum chemistry). Descriptive summary statistics for the change from baseline to each study visit will be presented. These descriptive summaries will be presented by test group, laboratory test and treatment group. Change from baseline will only be summarized for subjects with both baseline and post baseline.

For each parameter, the maximum change from baseline within each study period will be evaluated analogously.

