### **2.8.1 Adverse events (AEs)**

The crude incidence of treatment emergent adverse events (TEAEs) (i.e., events started after the first dose of study treatment or events present prior to the first dose of study treatment but increased in severity based on preferred term and on or before last dose date + 84 days) will be summarized by primary system organ class and preferred term. Confidence intervals for the crude rate will be derived. In addition, exposure-adjusted incidence rates including 95% CI will be provided for the entire treatment period. A graphical display of the crude incidence rates and exposure-adjusted incidence rates will be presented for all AEs and serious AEs by system organ class.

Adverse events reported will be presented in descending frequency according to their incidence in total secukinumab group (combining all secukinumab treatment groups), starting from the most common event. Summaries (crude incidences only) will also be presented for AEs by severity and for study treatment-related AEs. If a particular AE 'severity' is missing, this variable will be listed as missing and treated as missing in summaries. If a subject reported more than one adverse event with the same preferred term, the adverse event with the greatest severity will be presented. If a subject reported more than one adverse event within the same primary system organ class, the subject will be counted only once with the greatest severity at the system organ class level, where applicable.

Separate summaries will be provided for adverse events suspected to be related to study drug, deaths, serious adverse events, adverse events leading to discontinuation, and adverse events leading to temporary dose interruption.

Adverse events will also be reported separately by SMQ according to MedDRA, using a narrow search. The MedDRA version used for reporting the study will be described in a footnote.

Non-treatment emergent adverse events will be listed.

For SAEs that occurred during screening, a listing will be prepared for all subjects screened including screening failures.

When adjudication is required of major cardiovascular events, a summary of those types of events as reported by the investigator and confirmed by adjudication will be provided.

An overview of the safety analyses which will be performed for treatment emergent AEs, on-treatment laboratory tests and vital signs for each analysis period is described below.

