### 2.8.3.4 Compound specific safety evaluation

Safety topics of interest, such as risks defined in the Safety Profiling Plan (SPP), Risk Management Plan (RMP) or topics of interest regarding signal detection or routine analysis are defined in the Program Case Retrieval Sheet that is stored in CREDI at the path Cabinets/CREDI Projects/A/AIN457A/Integrated Medical Safety.

The crude incidence and exposure-adjusted incidence rates for SPP risks will be summarized. In addition, listings will be provided presenting which subjects experienced which risk.

Important note: For the evaluation of SPP risks, primary and secondary system organ classes and preferred terms of the MedDRA dictionary will be considered, as defined in the Program Case Retrieval Sheet and RMP.

[REDACTED]

[REDACTED]

[REDACTED]

[REDACTED]

[REDACTED]

[REDACTED]

[REDACTED]

[REDACTED]

[REDACTED]

[REDACTED]

[REDACTED]

[REDACTED]

[REDACTED]

[REDACTED]

[REDACTED]

[REDACTED]

[REDACTED]

[REDACTED]

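### Exposure-adjusted SAE rates can count events that fall after person-time has stopped, for subjects whose last visit comes before last dose + 84 days

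*SAP*

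**What the plan says.** **Denominator.** SAP 2.4.1 runs exposure from first dose "to the minimum of (last dose of the treatment + 84 days) and (last visit date". It then converts days to years and to the reporting unit: "Duration of exposure (100 subject years) = duration of exposure (years) / 100".

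**Numerator.** SAP 2.8.1 treats an event as treatment-emergent if it started after the first dose, or was already present but "increased in severity based on preferred term and on or before last dose date + 84 days". The last visit plays no part. The on-treatment windows for laboratory data (SAP 2.8.2) and vital signs (SAP 2.8.3.1) also end 84 days after the last dose, without a visit limit.

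**Where the two meet.** SAP 2.8.1 states that "exposure-adjusted incidence rates including 95% CI will be provided for the entire treatment period", and SAP Table 2-1 applies this to AEs and SAEs. SAP 2.8.3.4 adds: "The crude incidence and exposure-adjusted incidence rates for SPP risks will be summarized". Protocol 9.5.3 says that, as appropriate, "the incidence of AEs will be presented per 100 subject years of exposure".

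**Collection.** Protocol 7.2.2 requires every SAE after consent to be reported "until 20 weeks following the last administration of study treatment or until the end of study visit (whichever is later". Protocol 7.1 defines adverse events only up to the end of study visit. Later events that seem related go into the site's source documents, and only the serious ones go on to the sponsor.

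**The concern.** A rate per 100 subject-years is meaningful only if an event can be counted exactly when the subject is contributing time. Here a subject can stop contributing time at the last visit and still contribute an SAE up to 84 days after the last dose. The 20-week reporting duty means that such an SAE is meant to reach the sponsor.

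The rates concerned are those for SAEs and deaths, and those for any SPP risk defined by serious events. The bias runs upward and grows with the share of subjects who leave early. The gap also differs between the drugs, because the end-of-treatment visit for early leavers is set 4 weeks after the last secukinumab dose but 2 weeks after the last GP2017 dose. Equal drop-out would therefore not cancel it exactly.

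**Working it through.** The plan states no exposure-adjusted rate, so there is no figure of its own to reproduce. The check compares the two windows and then sizes the effect.

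**Inputs from the documents**
- Last planned dose: Week 100 for secukinumab (700 days after first dose) and Week 102 for GP2017 (714 days) (Protocol 5.2).
- Event window: last dose + 84 days, so 784 days for secukinumab and 798 days for GP2017 (SAP 2.8.1).
- Week 104, F112 and F120 fall at 728, 784 and 840 days.
- End-of-treatment visit for early leavers: 28 days (secukinumab) or 14 days (GP2017) after last dose (Protocol section 6).

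**Assumptions.** The share of an arm that leaves early is 5%, 10% or 20%; the last dose of leavers is at Week 52 (day 364); the event rate is constant; and the denominator is the SAP 2.4.1 duration, not cut at the first event. The visible text gives a formula for crude incidence only (SAP 5.4.4), so the link to 2.4.1 rests on the shared unit of 100 subject-years.

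**Step 1: gap per subject** = (last dose + 84) − min(last dose + 84, last visit)

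| Last visit | Secukinumab | GP2017 |
|---|---|---|
| F120 | 784 − 784 = 0 days | 798 − 798 = 0 days |
| F112 | 784 − 784 = 0 days | 798 − 784 = 14 days |
| Week 104 / end of treatment | 784 − 728 = 56 days | 798 − 728 = 70 days |
| Day of last dose | 84 days | 84 days |

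An early leaver who attends the end-of-treatment visit and nothing later has the same gaps: 84 − 28 = 56 days and 84 − 14 = 70 days.

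**Step 2: one subject.** With last dose and last visit both at Week 52, events are counted over 364 + 84 = 448 days against 364 days of exposure, a ratio of 448/364 = 1.23. At Week 12 it is 168/84 = 2.0.

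**Step 3: a whole arm.** Let s be the share of leavers, T the full window (784 or 798 days) and v the days from last dose to last visit. If all later SAEs are captured:

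inflation = [(1 − s)·T + s·448] / [(1 − s)·T + s·(364 + v)]

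For secukinumab with s = 20% and v = 0: (627.2 + 89.6)/(627.2 + 72.8) = 716.8/700.0 = 1.024.

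| Leavers | Secukinumab, v = 0 | GP2017, v = 0 | Secukinumab, v = 28 | GP2017, v = 14 |
|---|---|---|---|---|
| 5% | 1.0055 | 1.0054 | 1.0037 | 1.0045 |
| 10% | 1.0113 | 1.0111 | 1.0075 | 1.0093 |
| 20% | 1.0240 | 1.0236 | 1.0159 | 1.0196 |

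Moving the leavers' last dose between Week 12 and Week 78 shifts the 20% figure for v = 0 only between about 1.022 and 1.026.

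**Step 4: partial capture.** If a fraction c of the later events is recorded, secukinumab at 20% and v = 0 gives (700.0 + 16.8c)/700.0: 1.012 for c = 0.5, 1.006 for c = 0.25 and 1.000 for c = 0. At c = 0, lengthening the denominator alone would give 700.0/716.8 = 0.977, an understatement of about 2.3%.

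**Step 5: between drugs.** With 20% leaving each arm after the end-of-treatment visit, the secukinumab to GP2017 rate ratio is multiplied by 1.0159/1.0196 = 0.996, a distortion of about 0.4%.

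**The case against.** The strongest reply is that stopping person-time at the last visit is right for events that are not observed afterwards. That stands for non-serious AEs. Their collection ends at the end of study visit (Protocol 7.1), and a subject who does not come back yields few of them. Step 4 shows that lengthening the denominator for such events would bias their rates downward.

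It is also true that the plan works to close the gap. Early leavers are asked to attend the end-of-treatment visit, F112 and F120, and anyone reaching F120 has identical windows because the rule takes a minimum. The safety summaries are descriptive, with no hypothesis test. None of this answers the case of an SAE or death after the last visit.

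Three stronger readings are tempting but not supported:

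- **All AE rates are overstated.** A reader might infer this from the telephone follow-up in Protocol section 6: "If the subject refuses to return for these assessments or is unable to do so, every effort should be made to contact him/her". The sentence goes on to give the aim of the call, which is to learn why the subject will not return. It is not an AE collection call. After withdrawal of consent, further contact is barred unless safety findings require it (Protocol 5.6.3).
- **Home dosing makes exposure end months before the last dose.** This requires last visit to mean last attended site visit. The footnotes to Protocol Tables 6-1 and 6-2 call home-dosing occasions visits. The runs of optional visits long enough to matter most lie between Weeks 24 and 40 and between Weeks 76 and 92; around mid-study, site visits are due at Weeks 40, 52 and 64.
- **The SPP risks affected are known.** SAP 2.8.3.4 places their definitions in an external retrieval sheet, so the documents do not show which of them rest on serious events.

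**Conclusion.** The mismatch is real but narrow. It concerns subjects whose last visit precedes last dose + 84 days, and events reportable whether or not they attend: SAEs, deaths and any SPP risk built on them.

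The arm-level overstatement is at most about 0.5% with 5% leavers and about 2.5% with 20%, and less if later events are only partly recorded. The shares are assumptions. The 80% in Protocol 9.7 refers to completing treatment with evaluable films, not to leaving without a further visit, so 20% is a generous ceiling. The size also assumes a constant event rate and no cut at first event. Serious events clustering around departure would raise it, and the documents give nothing from which to size that. This is a minor point and touches no efficacy result.

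**What to change.** In SAP 2.4.1 and 2.8.1, state one end date that applies to both numerator and denominator of each exposure-adjusted rate:

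- **SAEs and deaths:** last dose + 84 days, cut at death or withdrawal of consent. This lies inside the 20-week reporting period.
- **Non-serious AEs:** the earlier of last dose + 84 days and the later of last visit and last recorded dose. Exposure then never ends before the last recorded dose, however last visit is read.
- **Rates that mix the two:** the non-serious end date is the safer choice, since both kinds of event are collected up to it.

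Do not use the date of last documented contact. Contact attempts are kept in source documents, and an SAE report is itself a contact, so the end date would depend on the outcome.

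The cost is one extra derivation and a footnote naming the window under each table. Crude incidences and listings can stay as planned. SAE rates become very slightly lower. If SAEs of subjects who left go unreported despite Protocol 7.2.2, the longer denominator would understate their rate a little (Step 4).
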